Nicotine is the primary addictive constituent within tobacco that supports the initiation, development, and persistence of smoking behavior. Nicotine serves as a primary reinforcer; for instance, it supports self-administration in both animal and human models (Corrigall, 1992; Corrigall & Coen, 1989; Goldberg et al., 1981; Henningfield & Goldberg, 1983; Rose & Corrigall, 1997). In addition, nicotine appears to be a strong secondary reinforcer, such that initially neutral stimuli that become closely associated with nicotine delivery obtain reinforcing properties (Caggiula et al., 2001; Goldberg et al., 1981; Palmatier et al., 2007). Those secondary (conditioned) reinforcement properties can be attained by sensory (taste, smell, and feel) aspects of smoking (Rose & Levin, 1991), as well as by a variety of exteroceptive stimuli and interoceptive (e.g., mood) states (Oliver et al., 2013).

Nicotine withdrawal is a constellation of subjective/emotional, behavioral, and cognitive disturbances experienced by smokers upon removal of nicotine after an extended period of use. It is important to consider that some symptoms of nicotine withdrawal can onset quite rapidly (within 30 minutes) upon ceasing tobacco use (Hendricks et al., 2006), and that withdrawal is a major impediment to successful cessation outcomes among those attempting to quit. Hence, it is not surprising that pharmacological approaches toward smoking cessation attempt to counteract the disruptive effects of nicotine withdrawal during the quitting process, either by directly replacing nicotine (e.g., gum, patch, inhaler, nasal spray, lozenge), or by addressing the neurochemical actions of nicotine in the brain (e.g., bupropion, varenicline). Given the best long-term smoking cessation rates with pharmacological and/or behavioral treatments rarely exceed 30-35%, there is clearly room to consider other pharmacological and/or behavioral approaches to cessation.

Reduced Nicotine Content and Public Health

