Surprisingly, none of the prior VLNC treatment studies emphasized strategies that would maximize extinction to cigarette-related reinforcement during the pre-quit period. Theoretically, the sub-threshold nicotine doses with VLNC cigarettes should extinguish both primary and secondary sources of smoking-related reinforcement. The proposed research will develop a behavioral intervention intended to optimize the efficacy of VLNC cigarettes from a learning-based (extinction) perspective. Specifically, the proposed project will (1) develop a theory-driven "facilitated extinction" intervention for use with VLNC cigarettes during the pre-quit period, (2) evaluate the efficacy of pre-quit VLNC cigarette smoking as a cessation strategy by conducting a randomized controlled trial (RCT), and (3) obtain data regarding potential mechanisms that may moderate or mediate treatment effectiveness, to inform future implementation of this novel cessation strategy. If successful, future research may continue to validate this VLNC treatment strategy in comparison with existing methods (e.g., NRT treatment), and determine the most effective methods to disseminate VLNC cigarettes for clinical benefit. Below, we discuss the theoretical foundations of the proposed research.

Facilitated Extinction

Recent advances in learning theory, along with methods from basic and applied research from other domains of psychopathology, can be used to optimize extinction as part of an approach to smoking cessation (e.g., Bouton, 2000; Conklin & Tiffany, 2002; Foa 2011; Laborda et al., 2011). We are currently evaluating such an approach to maximize extinction with extended pre-cessation varenicline. Following strategies employed in that project, we plan to base our initial development of a facilitated extinction workbook for pre-quit VLNC use on the following key techniques:

- a) Ensure that participants continue to smoke VLNC cigarettes at their normal rate during the pre-quit period. This will create maximum opportunities for extinction learning. Thus, premature smoking reduction or cessation will be actively discouraged (in contrast to ongoing smokers who may spontaneously reduce smoking when given VLNC cigarettes).

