Based on participant and counselor feedback from Study 1, the FE workbook was converted to a series of weekly booklets. The content is similar to what was included in the pilot study, but the workbook series now includes additional cessation-related advice and enhanced graphics. The targeted intervention will consist of the FE workbook series and supportive counseling (as developed and refined in Study 1), whereas the standard intervention will consist of the "Clearing the Air" booklet (National Cancer Institute; NIH Publication No. 11-1647), along

with a brief study introduction booklet which will explain the rationale for using reduced nicotine cigarettes as a cessation aid. Additionally, the standard intervention will entail an equal duration (relative to targeted intervention) of cognitive-behavioral smoking cessation counseling that follow recommendations from the USPHS Clinical Practice Guidelines along with supplemental handouts (Fiore et al., 2008). Counseling sessions for all conditions will include discussion of compliance with smoking only study cigarettes, as well as other study procedures. Although all participants will be strongly encouraged to smoke only study cigarettes, they will be told there is not a penalty for use of non-study cigarettes, and that it is crucial for them to report any use of non-study cigarettes or other nicotine or tobacco products. The VLNC immediate and gradual tapering conditions will be as described above, with participants, counselors and experimenters blind as to condition assignment.

Target Quit Date Participants will attend a session on their Target Quit Date. During this visit, all study cigarettes distributed during their prior visit will be collected, additional cessation counseling will be provided, physiological measures (i.e., carbon monoxide, breath alcohol, blood pressure, and heart rate) will be collected, and possible health changes will be assessed. Participants will also complete a Cigarette Evaluation Scale for their study cigarettes, the QSU for their study and usual brand cigarettes, the Drug Effects/Liking Scale for their study cigarettes to obtain intermediate smoking-related outcomes: cue-reactivity and cigarette purchase task (see descriptions below). Lastly, those randomized to the targeted intervention will be provided with the final Countdown booklet.

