Intermediate Outcomes (Aim 3). Intervention effects on proximal smoking outcomes (as indicators of potential effects on long-term outcomes) will be assessed using two validated tasks:

1) Cue Reactivity: The cue reactivity task will assess the effect of VLNC cigarettes and facilitated extinction techniques on cue-provoked cravings. A validated picture-viewing paradigm will be used to assess cue reactivity (e.g., Brandon et al., 2011; Brandon et al., in press). Twelve (12) smoking-related and 12 neutral control images will be randomly presented to each participant while craving measures are obtained. Smoking cues will include photos that have elicited substantial craving reports in our prior research. Neutral cues will consist of pictures from the International Affective Picture System (IAPS; Center for the Study of Emotion and Attention 1995) or other standardized picture sets or internet sources, and will include objects, people and situations that have been rated as neither pleasant, unpleasant, or arousing. Different sets of pictures will be counterbalanced across the two cue reactivity assessments to minimize familiarization. During the baseline and target guit date visits, participants will be instructed to view the 24 pictures on a high resolution computer monitor located 2.5 ft. in front of them, for 6 seconds each. Participants will be instructed to watch each picture for the entire time that it is displayed. Following picture offset, subjective smoking craving ratings will be obtained on a visual-analog scale. The cue reactivity assessment will take approximately 12 minutes to complete.

2) **Cigarette Purchase Task:** This task will be used to assess the reward value of cigarettes throughout the treatment period. Participants will be asked to report the number of cigarettes that they would hypothetically consume in a day at various costs (Jacobs & Bickel, 1999). This task will be completed by participants each week; the study cigarette version will be administered after the screening/baseline visit and through the follow-up phase, while the usual brand cigarette version will be administered at every visit (inclusive of the screening/baseline session). Several indices of demand are generated from the raw values, including demand

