Sample Size Determination. The planned sample size (n=20) for the developmental pilot study (Study 1; Aim 1) is based on considerations of practicality and usefulness. A primary focus of Study 1 will be on evaluation of feasibility (acceptability, demand, practicality) of the procedures, and determining potential improvements to incorporate into the subsequent RCT (Study 2). In the context of the goals and project timeline, the planned sample size for the developmental pilot study should provide the team with ample information to inform the RCT (Study 2). The planned sample size (n=208) for the RCT (Study 2) is based on considerations of statistical power and anticipated effects for the primary hypothesis regarding treatment outcomes (Aim 2). We assume those who receive the standard intervention (n=104) will achieve a 20% 7-day point prevalence abstinence rate at the 6-month follow-up. Based on an intent-totreat data analytic approach and a two-sided alpha = .05, the proposed sample will have .80 power to detect approximately an 18% improvement in abstinence rate among those who receive the targeted intervention. This magnitude of improvement would be clinically significant. and worthy of further refinement and application. A similar magnitude of effect would be detectable as a function of tapering schedule. No interaction effects (between intervention and tapering schedule) are predicted. Power is likely to be greater for detecting treatment effects on dichotomous cessation outcomes at the 2-month follow-up, continuous cessation outcomes at both follow-up timepoints, and intermediate (proximal) behavioral outcomes (Aim 3). Moreover, within-condition correlations as small as 0.28, and total-sample incremental R^2 as low as 0.07 (based on six predictors) would be detected, suggesting that the moderator analyses (Aim 4) would be adequately powered to detect clinically significant effects.

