Protection Against Risk: In order to protect participant confidentiality, all references to specific individuals are removed from files stored on computer media, and code numbers are assigned to all written and computer-stored research data. Participant names will only appear on signed Informed Consent documents, and on a separate study log, both of which will be stored separately from all research data in a locked cabinet. All participants will be informed that they may withdraw from the study at any time without penalty. The level of nicotine withdrawal associated with overnight smoking abstinence is typically not severe, and participants will be informed of potential symptoms they may experience. Similarly, the risks of nicotine withdrawal and craving during a smoking cessation attempt will be described to participants, and should be mitigated by pre-quit tapering of nicotine levels in study cigarettes. Suggestions for further minimizing withdrawal symptoms will be instructed to call the PI, smoking cessation counselor, or study physician (or licensed medical professional designated to consult in his absence) in the event of excessive side effects while smoking VLNC cigarettes or after the TQD.

Participants who endorse negative mental health changes or suicidal ideation at any visit will complete the Prime MD at that session. Indications of major depressive disorder or other psychiatric conditions will trigger administration of the BDI, which will be reviewed by the LMP and/or PI. An 'Adverse Event Form' and 'Blood Pressure and Heart Rate Symptom Checklist' will be completed and brought to the LMP (or PI/Co-I in lieu of LMP) if an automatic and subsequent manual heart rate measurement during the same visit is out of range (blood pressure at or above 160/100 or below 90/50; heart rate at or above 105 bpm or below 45 bpm).

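### The cue-reactivity task sets no pre-session smoking condition and no time of last cigarette is recorded, so an Aim 3 craving difference cannot be cleanly read as reduced cue reactivity

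*Combined protocol and SAP*

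**What the plan says.** Under Study 2, Intermediate Outcomes (Aim 3), the cue task is given at baseline and on the target quit date. It uses 12 smoking and 12 neutral control pictures, each shown for 6 seconds, with picture sets counterbalanced across the two sessions. On measurement the text says: "Following picture offset, subjective smoking craving ratings will be obtained on a visual-analog scale". The stated purpose is to assess craving provoked by cues.

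The Target Quit Date section says that at this visit "all study cigarettes distributed during their prior visit will be collected", so participants may have study cigarettes with them until they arrive. That section and the Appendix tables of procedures by visit list carbon monoxide (CO), a Timeline Follow-Back, the smoking-urges questionnaire and rating scales. Neither gives a pre-session smoking instruction or a time of last cigarette. One row of the Appendix table has no readable name, but it is marked for Visit 1 only.

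Statistical Considerations, Aim 3, names self-reported craving in response to smoking cues as the index and tests intervention and tapering schedule. It states no neutral-cue contrast and no term for CO or recent smoking.

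**The concern.** Craving depends on how long ago a person last smoked as well as on the picture. Section B of the protocol (Nicotine and Smoking Cessation) notes that "some symptoms of nicotine withdrawal can onset quite rapidly (within 30 minutes) upon ceasing tobacco use". The second cue task falls on the quit date itself, when one participant may have smoked on the way in and another may have stopped the evening before. The Visit 1 task has no smoking condition either, so change from baseline carries the same uncontrolled variable at both ends.

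Two other passages sharpen the question. Section E, Protection Against Risk, says: "The level of nicotine withdrawal associated with overnight smoking abstinence is typically not severe". No visit procedure asks for overnight abstinence, so staff cannot tell from the document in what state participants should arrive. The pre-quit instructions also differ by arm. Under Facilitated Extinction, item a, the targeted arm is to keep smoking at its usual rate and "premature smoking reduction or cessation will be actively discouraged", whereas the standard arm receives guideline-based cessation counselling.

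What is at stake is the interpretation of Aim 3. Its results are meant to shed light on mechanism and to help decide which tapering schedule to take forward.

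**Working it through.** **The plan's own power figure.** The only powered comparison is 6-month abstinence. Inputs from Sample Size Determination are 104 per intervention level, a standard arm that "will achieve a 20% 7-day point prevalence abstinence rate at the 6-month follow-up", and "two-sided alpha = .05, the proposed sample will have .80 power to detect approximately an 18% improvement in abstinence rate". Solving for the detectable difference gives 17.5 points (pooled-variance normal approximation) or 18.5 points (with continuity correction). The stated figure is reproduced. No figure is given for cue reactivity; the text says only that power for intermediate outcomes is likely to be greater.

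**Detectable craving difference at the quit date.** The note to Table 2 expects 158 at this session, so 158 / 2 = 79 per level of either factor. In SD units:

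(1.960 + 0.842) × √(2/79) = 2.802 × 0.1591 = 0.446 SD.

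**Noise if deprivation is balanced between arms.** The documents give no craving SD and no deprivation effect, so these inputs are assumptions: a share f = 0.5 arrives abstinent, with craving higher by D = 0.5 to 1.0 SD.

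- Variance: V = 1 + f(1 − f)D². For D = 0.5, V = 1 + 0.25 × 0.25 = 1.0625. For D = 1.0, V = 1 + 0.25 × 1 = 1.25.
- Power at 0.446 SD: Φ(2.802/√V − 1.960).
- D = 0.5: 2.802/1.0308 = 2.718; 2.718 − 1.960 = 0.758; power .776.
- D = 1.0: 2.802/1.1180 = 2.506; 2.506 − 1.960 = 0.546; power .707.

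In sample-size terms, 79/1.0625 = 74 and 79/1.25 = 63 effective participants per level. This treats the index as the raw smoking-cue rating at the quit date and gives no credit for the Visit 1 rating.

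**What the neutral pictures could remove.** Write a smoking-picture rating as s + a and a neutral-picture rating as n + a, where a is the general craving brought into the session. The difference is s − n, so any part of deprivation that raises both ratings equally drops out. The data for this contrast are already collected, but the Aim 3 text does not specify it. A deprivation effect that is larger for smoking pictures would not cancel.

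**Is a difference between arms documented?** The targeted-arm instruction concerns smoking rate over the pre-quit weeks, and neither arm's instruction for the hours before the quit-date visit is given. Both arms have the same quit-date timing and return cigarettes at that visit. An imbalance is plausible from the differing instructions, but nothing establishes it. For immediate versus gradual taper, which is crossed with intervention, the documents suggest no such route, so only the noise argument applies.

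**The case against.** The strongest reply is that the task has its own control condition and that recent smoking is not wholly unmeasured. Both points stand in part. The neutral pictures could absorb general craving, but only if the contrast is the planned index. CO and the quit-date Timeline Follow-Back are indirect: CO also reflects the amount smoked, neither is described as giving time since last cigarette, and neither enters the Aim 3 models. The forms' individual fields are not in the documents.

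A second reply concerns the 30-minute remark, which describes removal of nicotine after extended use. By the quit date participants have been assigned .03 mg cigarettes for one week (gradual) or four weeks (immediate), below the .17 mg threshold the protocol cites. Hours since such a cigarette may matter less than the remark suggests. This stands, and it is why the 0.5 to 1.0 SD input is only an assumption.

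A reader might also infer that the Aim 3 test is biased. An assumed gap of 15 to 20 points in the share arriving abstinent would shift mean craving by 0.15 × 0.5 = 0.075 SD to 0.20 × 1.0 = 0.20 SD, and a nominal 5% test would then reject about 7% to 20% of the time. The documents do not support calling this type I error. The gap has no source in them, and a deprivation difference caused by the assigned instructions is a consequence of randomised treatment and so part of the total effect.

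Nor do the documents support reading the overnight-abstinence sentence as a study requirement. It is one general risk statement tied to no visit.

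**Conclusion.** The gap is real and worth closing, but it limits interpretation of a secondary aim; it is not a flaw in the randomised comparison. As written, time since last cigarette is neither standardised nor recorded at either cue task, and it could not be reliably recovered later. It adds noise to both Aim 3 contrasts. If it differs between the targeted and standard arms, a craving difference could not be read as reduced cue reactivity.

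The power loss from .80 to about .78 to .71 rests on assumptions: half arriving abstinent, a 0.5 to 1.0 SD effect, 79 per level, and the raw smoking-cue rating as the index. A smoking-minus-neutral contrast would remove whatever part of the deprivation effect is common to both picture types. The stronger readings, that the arms will differ, that the taper comparison is confounded or that the test's error rate is inflated, go beyond the documents. The abstinence outcome is untouched.

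**What to change.** 1. Give the same pre-session smoking instruction in all four arms for both the Visit 1 and quit-date cue tasks. The interval is for the investigators to set; it must be reconciled with the overnight-abstinence wording under Protection Against Risk.
2. Record the clock time and type of the last cigarette before each task, beside the CO already taken, and report it by arm.
3. Prespecify the smoking-minus-neutral craving contrast as the cue-reactivity index, using the neutral pictures already shown.
4. Add a supportive sensitivity analysis in the full sample that includes time since last cigarette and CO, labelled as adjusting for a post-randomisation variable. Do not restrict the analysis to sessions that met the instruction: that would select on something the assigned treatment may influence.

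The cost is one line in the visit reminder, one form field and a short addition to the analysis text. Some sessions will fall outside the instruction, and the sensitivity analysis can only aid interpretation; it does not replace the randomised comparison.
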